### PROTOCOL VERSION and AMENDMENTS

Protocol Version	Date	Change Initiated (Initials)	Brief description of protocol modification/actions requested, if any
Template V1	8/26/2020	[name]	Original
V2	9/21/2020	[name]	Corrected error in hypothesis statement, added [name], clarified definition of R-CECS to include pressure testing, clarified recruitment
V3	5/2/2021	[name]	Reviewed and updated for IRB comments
V4	8/3/2021	[name]	Reviewed and updated for IRB comments

## List of Abbreviations

Version #: 3

[figure not shown]
### Study Summary

## ONABOTULINUMTOXINA (BOTOX) EFFECT ON PAIN AND FUNCTION IN RECURRENT CHRONIC EXERTIONAL COMPARTMENT SYNDROME: A PILOT STUDY

Title	OnabotulinumtoxinA (Botox) effect on pain and function in recurrent chronic exertional compartment syndrome: a pilot study
Short Title and Precis	Botox for the treatment of recurrent chronic exertional compartment syndrome
Methodology	Open label pilot study
Study Duration	2 years
Study Center(s)	University of Wisconsin Hospitals and Clinics
Objectives	Determine effect of Botox on pain and function using the University of Wisconsin Running Index
Number of Subjects	10 subjects consisting of 20 legs
Diagnosis	Recurrent chronic exertional compartment syndrome (R-CECS)
Main Inclusion Criteria	Patients greater than 18 years of age with diagnosis of R-CECS
Main Exclusion Criteria	Diagnosis other than CECS
Study Product, Dose, Route, Regimen	Botox (reconstituted at 100 units/mL) to be injected under standard palpatory technique into the affected lower leg compartment. Dosage will be based upon the affected muscles
FDA status of product	FDA approved
Duration of administration	6 month follow up time after injection of medication. Typical duration of action of Botox is 10-12 weeks
Reference therapy	No direct comparison
Statistical Methodology	Using a one-way ANOVA and assuming independence of leg scores for each patient, we will have 80% power to detect an overall significant F-test (assuming a 2 (SD=1) point decrease in pain score from baseline to 6 months) with n=6 patients (e.g. 12 legs). Accounting for potential drop-out (15%) and, additionally, adjusting for non-parametric analyses, n=10 patients (e.g 20 legs) will be sufficient to provide preliminary effect sizes at each time point which will help inform power analyses for studies planned beyond this pilot study.

## Schematic of Study Design

Flow diagram or study calendar (e.g., randomized controlled trial)

## 2. Background and Introduction

This document is a protocol for a human research study. This study is to be conducted according to US and international standards of Good Clinical Practice, applicable government regulations, and Institutional research policies and procedures.

### 2.1 Background and Rationale

Chronic exertional compartment syndrome (CECS) is an overuse injury first described by Mavori in 1956 that typically affects young endurance athletes, classically distance runners. CECS occurs primarily in the

lower leg, predominantly in the anterior compartment, although it has been reported elsewhere in the bodyii,iii,iv,v,vi.

The pathophysiology of CECS is not completely understoodvii,viii,ix. Similar to acute compartment syndrome, it is thought to result from increased pressure within the restrictions of the fascial planes of a muscle compartment. Exercise increases blood flow to active muscles causing them to expand. If constricted by surrounding noncompliant fascia, such swelling increases pressure within the muscle compartment. Ultimately, pressure within the compartment reduces blood flow leading to muscle ischemia and pain when metabolic demands cannot be met. Several studiesx have demonstrated decreased blood flow and oxygenation in the legs of symptomatic patients with CECS.

Cessation of inciting activities resolves symptoms in most cases of CECS. Without this cessation, the prognosis for CECS is poor if treated non-operatively. Should symptoms continue, patients are referred for possible muscle compartment release, currently the most widely accepted treatment approach despite a significant number of treatment failuresx,xi,xii. To date, no alternative non-operative approach has successfully treated refractory symptomsii,viii,xiii,xiv.

Recently, it has been hypothesized that botulinum toxin could reduce intramuscular pressure in CECSxv. Isner-Horoboti et alxv, performed abobotulinum toxin A injections into the anterior and anterior/lateral compartments in 16 individuals with a mean follow up of 4.4 months (range 3-6 months). Fifteen (95%) patients were asymptomatic after intervention with fourteen (88%) exhibiting normalized postexercise compartment pressures. Using manual muscle testing, they determined that 11 patients displayed decreased strength though did not produce noticeable subjective weakness. A later case report by Baria and Sellonxvi presented the first long-term follow up (14 months) of a CECS case treated with botulinum toxin injections (Botox) in which the patient reported continued pain relief and had resumed her active lifestyle without adverse effects. Finally, Hutto et alxvii demonstrated 11 months of pain relief following botulinumtoxin injection in a military recruit for CECS.

The proposed investigation will aim to build upon the results of existing studies. The novelty of our approach involves a differing dosage of the toxin (Botox) into a more targeted muscle group. Further, while previous studies have used manual muscle testing to test strength, many studies have found this method unreliable. As such, we will be using the Kiiro force sensor at multiple time points to determine weakness quantitatively. We will be utilizing the reliable and validated University of Wisconsin Running Index to evaluate return to sport. Finally, and most importantly, we will be treating a group of patients (R-CECS) for whom no current treatment is available. To date, there are no published articles on using Botox to treat R-CECS although, in clinic, the PI has treated an individual with great success utilizing this approach.

## 2.2 Hypothesis

Hypothesis: Injection of Botox into the affected muscle group will alleviate pain associated with R-CECS.

## 2.3 Study Agent

OnabotulinumtoxinA (Botox) does not have FDA approval for the proposed use. It does have FDA approval for spasticity in both upper and lower extremities, cervical dystonia, bladder dysfunction, chronic migraine, primary axillary hyperhidrosis, blepharospasm, and strabismus.

Maximum dosage is not well defined; dosage is dependent upon treatment effect and indication. The maximum cumulative dose should generally not exceed 400 units in a 3-month interval when treating one or more indications.

Description:

Formerly known as botulinum toxin type A; IM toxin that reduces local muscle activity. Approved and off-label uses include cervical dystonia, blepharospasm, strabismus, upper limb spasticity, lower limb spasticity, facial wrinkles, migraine prophylaxis, cerebral palsy, low back pain, excessive sweating, overactive bladder, and urinary incontinence associated with neurologic conditions. Distant spread of botulinum toxic effects from the site of injection has resulted in symptoms suggestive of systemic

botulism (including respiratory compromise and death) after the use of botulinum toxins types A and B. Botulinum toxins types differ and different types are not exchangeable or substitutable for one another.

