### **2.6 Dose Rationale**

Dosing considerations were made in looking at previous studiesxv,xviii as well as medical expertise of the investigators. A previous studyxviii have injected 40 units (20 proximal and 20 distal) into the each the TA, extensor digitorum longus, and extensor hallucis longus. Our protocol changes this dosing to the following:

- 50 units total (25 proximal and 25 distal) into the TA for anterior symptoms
- 50 units in to the peroneal longus for the lateral compartment
- 50 units into each the medial and lateral gastrocnemius for superficial posterior symptoms
- 50 units into the tibialis posterior for deep posterior symptoms

We chose a dosage on the low end recommended by the previous studies for hypertonicity in the respective muscles in conjunction with the investigator's clinical expertise. To ensure placement of the medication into the proper muscle, we will be using standardized palpatory techniques as is common in Botox injections for spasticity. A single injection will be performed in this study as previous studies have shown prolonged pain relief despite a known

duration of action of the medication to be 2-6 months to help determine the duration of relief in this diagnosis. Given this duration of action, most side effects associated with muscle weakness are temporary and resolve over time.

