### **6.4 Route of Administration**

- Dose will be determined based upon patient location of symptoms as follows:
  - - 50 units total (25 proximal and 25 distal) into the TA for anterior symptoms
  - - 50 units in to the peroneal longus for the lateral compartment
  - - 50 units into each the medial and lateral gastrocnemius for superficial posterior symptoms
  - - 50 units into the tibialis posterior for deep posterior symptoms
- Treatment duration: Established duration of action on muscular weakness of other uses of Botox is between 2 and 4 months. Given this novel treatment, duration of action in our study is unknown.
- Expected side effects include:
  - Weakness in the muscle injected
  - Injection site pain
  - Injection site bleeding

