### **6.6 Dose Adjustments/Modifications/Delays**

Following injection, dosage cannot be changed and study will maintain the aforementioned dose for the duration of this study. Based on studies for other indications, Botox has been shown to take effect in approximately 2 weeks and last between 2 and 4 months.

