#### 6.9.3 Dispensing

Drug will be ordered by the lead investigator prior to the scheduled clinic visit one. The drug will be prepared, assigned to the appropriate patient, and delivered to the UW Clinic at The American Center by the UW Pharmacy within 24 hours of the appointment. Regular study drug reconciliation will be performed to document drug assigned, drug consumed, and drug remaining. This reconciliation will be logged on the drug reconciliation form, and signed and dated by the study team.

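### Read per leg, the compartment dosing list can total 450 or 500 units in one session, above the protocol's own 400-unit guidance, with no cap or justification in the dosing or ordering sections

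*Combined protocol and SAP*

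**What the plan says.** Section 2.3 gives the only figure for total exposure: "The maximum cumulative dose should generally not exceed 400 units in a 3-month interval when treating one or more indications". The sentence before it is a qualifier: "Maximum dosage is not well defined; dosage is dependent upon treatment effect and indication". The same section describes distant spread of toxin effect, including respiratory compromise and death, and Section 2.7 lists this as a boxed-warning risk.

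Section 6.4 sets the dose: "Dose will be determined based upon patient location of symptoms as follows". The list, which is the same in Section 2.6, is:

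- anterior symptoms: 50 units into the tibialis anterior
- lateral compartment: 50 units into the peroneus longus
- superficial posterior: "50 units into each the medial and lateral gastrocnemius for superficial posterior symptoms", so 100 units
- deep posterior: 50 units into the tibialis posterior

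Neither section states whether the amounts are per leg or per participant, how many compartments may be treated, or what the total may be. The justification in Section 2.6 is muscle by muscle: "We chose a dosage on the low end recommended by the previous studies for hypertonicity in the respective muscles". Section 6.6 says that after injection "dosage cannot be changed and study will maintain the aforementioned dose for the duration of this study", and gives no rule for reducing a planned dose beforehand. Section 6.9.3 says "Drug will be ordered by the lead investigator prior to the scheduled clinic visit one", with no check on total units.

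**The concern.** An investigator who follows Section 6.4 exactly for a participant with extensive disease in both legs can exceed the figure in Section 2.3, and nothing in the dosing or ordering sections would flag it. Section 2.6 defends the amount per muscle and does not discuss the sum across muscles and legs, which is what the Section 2.3 guidance addresses.

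Several features of the trial make this worth settling in writing:

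- The use is not FDA-approved, and Section 2.5 reports no published experience in recurrent disease.
- Treatment is a single injection that cannot be withdrawn once given (Section 5.7.3).
- The principal investigator acts as data monitoring committee, medical monitor and study monitor, and no independent audits are planned (Sections 10.6, 11.1 and 11.1.1). A written limit would therefore not be duplicating another independent check.

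**Working it through.** The protocol gives no total per leg or per participant, so there is no stated figure to reproduce. The check is addition and a full enumeration.

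**Inputs**

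- Doses (Sections 2.6 and 6.4): anterior 50, lateral 50, superficial posterior 2 × 50 = 100, deep posterior 50.
- Legs per participant: 2, since the Study Summary counts 10 subjects as 20 legs.
- Sessions: one (Section 7.4.4), so the whole dose falls within one 3-month interval.
- Reference figure (Section 2.3): 400 units in 3 months.
- Assumptions: doses are per leg, and both legs are treated.

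**Step 1. One leg.** The maximum is 50 + 50 + 100 + 50 = 250 units. Four compartments give 2⁴ − 1 = 15 patterns with at least one affected:

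| Units in the leg | Patterns |
|---|---|
| 50 | 3 |
| 100 | 4 |
| 150 | 4 |
| 200 | 3 |
| 250 | 1 |

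**Step 2. Both legs.** There are 15 × 15 = 225 left/right pairs. Those at or above 400 units are:

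| Total | How reached | Pairs | Ratio to 400 |
|---|---|---|---|
| 400 | 200 + 200 (3 × 3 = 9), 250 + 150 (4 × 2 sides = 8) | 17 | 1.00 |
| 450 | 250 + 200 (3 × 2 sides) | 6 | 450/400 = 1.125 |
| 500 | 250 + 250 | 1 | 500/400 = 1.25 |

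So 6 + 1 = 7 of 225 pairs exceed 400 units, and 450 and 500 are the only totals above it.

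**Step 3. What triggers it.** The 450-unit pairs have all four compartments in one leg, and superficial posterior plus two of the other three in the other leg: 4 + 3 = 7 of 8 compartments. The 500-unit pair has all eight. When the same compartments are treated in both legs, the totals are 100, 200, 300, 400 or 500, so only all-compartment disease exceeds 400.

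**Step 4. Ordinary cases.** Anterior only, both legs: 2 × 50 = 100 units. Anterior plus lateral, both legs: 2 × 100 = 200 units.

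**Step 5. Alternative readings.** Read per participant, the maximum is 250 units and the guidance is never reached. The same maximum applies to anyone treated in one leg only.

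**The case against.** The strongest reply is that the number is already in the protocol, as soft guidance. Section 2.3 says the maximum is not well defined and that 400 should generally not be exceeded, so a rare participant at 450 or 500 would not breach an absolute rule. This stands: 400 is not a hard limit. But general guidance is properly exceeded with a reason, and none is given. Having the number in Section 2.3 also does not help when the operative rule in Section 6.4 can override it without comment.

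The trigger is also remote. Section 2.1 describes the condition as occurring "predominantly in the anterior compartment", much of the text speaks of a single affected compartment or muscle group, and the earlier series described in Section 2.1 treated anterior or anterior/lateral compartments. At this protocol's doses that is 100 to 200 units bilaterally. This stands too, and it limits the size of the point. It also means that the cited precedent does not cover four-compartment bilateral totals.

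The per-leg reading is not stated. True, but pain is measured in each leg (Section 4.1.1), and a per-participant reading would require splitting each dose between legs, for which there is no instruction. If that was the intention, the text still needs correcting, because the two readings differ two-fold when both legs have the same compartments treated.

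There are partial safeguards. Diagnosis requires elevated pressure after surgical release, prior botulinum toxin is an exclusion, the investigator may exclude at discretion, and drug is ordered by the lead investigator and assigned to each patient. None of these limits the total study dose. Section 2.7 refers to a package insert in an appendix that was not available for this check. The finding is therefore confined to what the dosing and ordering sections state, and they do not point to the insert for a cap.

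**Conclusion.** The concern holds. On the per-leg reading with both legs treated, the dosing list permits 450 or 500 units in one session, 50 or 100 units above the protocol's own guidance, and no dosing or ordering rule carries the limit forward or justifies exceeding it.

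The arithmetic is exact. What is uncertain is how often it would matter: 7 of 225 is a share of conceivable patterns, not a probability, and the documents give no distribution of affected compartments. Among 10 participants the number affected could well be zero. The point should be fixed because the possible harm is serious, the injection is irreversible and the remedy is cheap. It has no bearing on the endpoint, the sample size or the analysis.

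**What to change.** Amend Sections 2.6 and 6.4 to say that the listed doses are per leg, and that the total per participant across both legs and all compartments must not exceed 400 units. If the sponsor wishes to allow more, Section 2.6 should give the reason and the maximum.

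Add a rule, agreed between the investigators and the pharmacy, for which compartments to treat or how to reduce doses when the list exceeds the cap. The reduction needed would be 50 or 100 units. Put the participant total on the drug order in Section 6.9.3 so that it is checked before preparation.

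The cost is a short amendment and one line on the order form, with no change to visits, sample size or analysis. The downside is that a participant with very extensive disease would have a compartment untreated or under-dosed. That should be recorded by leg, because it could weaken the pain response in that leg.

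As a clerical matter, the injection row in Table 3 names only the tibialis anterior and should refer to the affected muscles.

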#### Mechanism of Action

OnabotulinumtoxinA blocks neuromuscular conduction by binding to receptor sites on motor nerve terminals, entering nerve terminals, and inhibiting the release of acetylcholine. Inhibition occurs as the neurotoxin cleaves a protein (SNAP-25) integral to the successful docking and release of acetylcholine from vesicles situated within nerve endings. After intramuscular injection of a therapeutic dose, onabotulinumtoxinA produces partial chemical denervation of the muscle resulting in a localized reduction in muscle activity. Additionally, the muscle may atrophy, axonal sprouting may occur, and extrajunctional acetylcholine receptors may develop. Evidence exists that suggests that reinnervation of the muscle may occur thereby slowly reversing muscle denervation produced by the neurotoxin.

A reduction in sialorrhea may also occur by blocking the liberation of acetylcholine in autonomic nerve terminals in the parotid and submandibular glands. There is no evidence of axonal sprouting and consecutive innervation in autonomic nerve fibers in sialorrhea studies.

For treatment of neurogenic bladder, after injection into the detrusor muscle the efferent pathways of detrusor activity are affected via inhibition of acetylcholine release; inhibition of afferent neurotransmitters and sensory pathways is also thought to occur. Therapy increases maximal bladder capacity, reduces maximum detrusor pressure, reduces incontinence episodes, and may reduce the need for anticholinergics in patients with neurogenic overactive bladder.

### **2.4 Summary of Relevant Preclinical Data**

### **2.5 Summary of Clinical Data**

Recently, it has been hypothesized that botulinum toxin could reduce intramuscular pressure in CECSxviii. Isner-Horoboti et alxv, performed abobotulinum toxin A injections into the anterior and anterior/lateral compartments in 16 individuals with a mean follow up of 4.4 months (range 3-6 months). Fifteen (95%) patients were asymptomatic after intervention with fourteen (88%) exhibiting normalized postexercise compartment pressures. Using manual muscle testing, they determined that 11 patients displayed decreased strength though did not produce noticeable subjective weakness. A later case report by Baria and Sellonxix presented the first long-term follow up (14 months) of a CECS case treated with botulinum toxin injections (Botox) in which the patient reported continued pain relief and had resumed her active lifestyle without adverse effects.

To date, there exists no published papers utilizing botulinumtoxin to treat R-CECS. However, in clinical practice, the PI has treated individuals with success utilizing this approach.

### **2.6 Dose Rationale**

Dosing considerations were made in looking at previous studiesxv,xviii as well as medical expertise of the investigators. A previous studyxviii have injected 40 units (20 proximal and 20 distal) into the each the TA, extensor digitorum longus, and extensor hallucis longus. Our protocol changes this dosing to the following:

- 50 units total (25 proximal and 25 distal) into the TA for anterior symptoms
- 50 units in to the peroneal longus for the lateral compartment
- 50 units into each the medial and lateral gastrocnemius for superficial posterior symptoms
- 50 units into the tibialis posterior for deep posterior symptoms

We chose a dosage on the low end recommended by the previous studies for hypertonicity in the respective muscles in conjunction with the investigator's clinical expertise. To ensure placement of the medication into the proper muscle, we will be using standardized palpatory techniques as is common in Botox injections for spasticity. A single injection will be performed in this study as previous studies have shown prolonged pain relief despite a known

duration of action of the medication to be 2-6 months to help determine the duration of relief in this diagnosis. Given this duration of action, most side effects associated with muscle weakness are temporary and resolve over time.

## 2.7 Potential Risk and Benefits to Subjects

### 2.7.1 Known Potential Risks

#### Immediate risks

- Pain during injection
- Infection of injection site
- Bleeding following injection
- Swelling at injection site

#### Long-range risks

- TA weakness resulting in foot drop
- Lateral compartment weakness resulting in eversion weakness
- Plantarflexion weakness resulting in weakness with plantarflexion
- Distant spread resulting in botulism-like symptoms including muscle weakness all over body, vision problems, difficulty speaking or swallowing, trouble breathing, loss of bladder control, respiratory compromise, death (see black box warning of Botox labelling)

#### Reproductive

- Injections will not be performed in individuals who are or who have a reasonable possibility of being pregnant.
- Should potential subjects be of unknown pregnancy status and wish to enroll in the study, a urine pregnancy test can be performed prior to enrollment.

